5.2.2. Derivations and Handling of Missing Baseline Data

| Definition | Reporting Details |
|------------------------|---|
| Change from Baseline | = Post-Dose Visit Value – Baseline |
| % Change from Baseline | = 100 x [(Post-Dose Visit Value – Baseline) / Baseline] |

NOTES:

- Unless otherwise specified, the baseline definitions specified in Section 5.2.1 will be used for derivations for endpoints / parameters and indicated on summaries and listings.
- Unless otherwise stated, if baseline data are missing no derivation will be performed and will be set to missing.
- The baseline definition will be footnoted on change from baseline displays wherever applicable.

5.3. Other Considerations for Data Analyses and Data Handling Conventions

Table 1 provides an overview of appendices within the RAP for outlining general considerations for data analyses and data handling conventions.

Table 1 Overview of Appendices

| Section | Component |
|---------|--|
| 11.2 | Appendix 2: Assessment Windows |
| 11.3 | Appendix 3: Study Phases and Treatment Emergent Adverse Events |
| 11.4 | Appendix 4: Data Display Standards & Handling Conventions |
| 11.5 | Appendix 5: Derived and Transformed Data |

CONFIDENTIAL

| Section | Component |
|---------|---|
| 11.6 | Appendix 6: Reporting Standards for Missing Data |
| 11.7 | Appendix 7: Values of Potential Clinical Importance |

6. STUDY POPULATION ANALYSES

6.1. Overview of Planned Study Population Analyses

The study population analyses will be based on the "Safety" population, unless otherwise specified.

All the displays will be split by part. Study population tables would be presented by cohort and a combined placebo (of all cohorts).

Table 2 provides an overview of the planned study population analyses, with full details of data displays being presented in Appendix 11: List of Data Displays.

Table 2 Overview of Planned Study Population Analyses

| Display Type | Data | Displays Gene | rated |
|---|-------|---------------|---------|
| | Table | Figure | Listing |
| Randomization | | | |
| Randomization | | | Υ |
| Subject Disposition | | | |
| Subject Disposition | Y | | Υ |
| Reason for Screening Failures | Y | | Υ |
| Reason for Withdrawals | | | Υ |
| Protocol Deviations | Y | | Υ |
| Inclusion and Exclusion Criteria Deviations | | | Υ |
| Study Populations | Y | | |
| Demography | | | |
| Demographics Characteristics | Y | | Υ |
| Race & Racial Combinations | Y | | Y |
| Medical Condition & Concomitant Medications | • | | |
| Medical Conditions (Current/Past) | Y | | Y |
| Concomitant Medications | Y | | Y |

NOTES:

6.1.1. Disposition and Withdrawals

All participants who provide informed consent will be accounted for in this study. In each study part, subject disposition will be tabulated for each study treatment and for all participants combined with the number of participants who are randomly assigned to treatment, complete the study and prematurely discontinue as well as the reason for early discontinuation. A listing will present dates of completion or early withdrawal and the reason for early discontinuation, if applicable, for each participant.

Listings of study eligibility, treatment randomization and study treatment administration will be provided for each study part based on the layout mentioned above.

[•] Y = Yes display generated.

6.1.2. Demographic and other Baseline Characteristics

Individual subject demographics and baseline characteristics (medical history and results from drug and alcohol screens, smoking/nicotine history) will be presented in listings for each study part.

Demographic characteristics such as age, sex, race, ethnicity, height, weight, and body mass index (BMI) will be summarized and tabulated by treatment and for all participants overall for each study part. Descriptive statistics will be presented for age, height, weight, and BMI. Frequency counts and percent will be presented for sex, race and ethnicity.

6.1.3. Medications

All prior and concomitant medications will be listed for each study part based on the layout mentioned earlier. Summaries of all medications taken during the course of the study will be presented in tabular form for each study part using GSK Drug Dictionary 1.3. The number and percentage of participants taking concomitant medications will be summarized by cohort and overall for each study part separately. For each participant, the medication will be counted only once within a given preferred drug name level. A participant may appear more than once if he/she has more than one concomitant medication coded under different categories, however, the participant will be counted only once in the overall category.

Please refer to Appendix 3: Study Phases and Treatment Emergent Adverse Events for definition of prior, concomitant and post-treatment medications. Handling of partial dates for medications is outlined in Appendix 6: Reporting Standards for Missing Data.

7. SAFETY ANALYSES

The primary safety analyses for this study will be based on the Safety population for each dose taken, analysed separately for study parts, unless otherwise specified.

Data will be listed and summarized according to GSK reporting standards, where applicable. Listings will be sorted by dose, participant and time; summaries will be presented by dose and time for different parts of the study. Participants receiving placebo may be combined into one treatment group in the summaries within each part.

For categorical variables, the population size (N for sample size and n for available data) and the percentage (of available data) for each class of variable will be presented. Continuous variables will be summarized using descriptive statistics, including N, mean, standard deviation (SD), median, minimum and maximum values.

Table 3 provides an overview of the planned safety analyses for each study part, unless otherwise specified, with full details of data displays being presented in Appendix 11: List of Data Displays.

Table 3 Overview of Planned Safety Analyses

| Endpoint | | Abs | olute | | (| Change fro | m Baselin | ie | | | |
|---------------------------------|---------|-----|-------|--------|-----|------------|------------|----|--|--|--|
| | Summary | | | ridual | Sum | mary | Individual | | | | |
| | T | F | F | L | T | F | F | L | | | |
| Exposure | | | | | | | | | | | |
| Extent of Exposure | Υ | | | Υ | | | | | | | |
| Adverse Events ¹ | | | | | | | | | | | |
| All AE's | Υ | | | Υ | | | | | | | |
| Serious AE's | Υ | | | Υ | | | | | | | |
| Treatment related AE's | Υ | | | Υ | | | | | | | |
| AE's leading to | Υ | | | Υ | | | | | | | |
| Withdrawal | | | | | | | | | | | |
| Laboratory Values | | | | | | | | | | | |
| Clinical Chemistry ² | Υ | | | Υ | Υ | | | | | | |
| Hematology | Υ | | | Υ | Υ | | | | | | |
| Coagulation | Υ | | | Υ | | | | | | | |
| Urinalysis | | | | Υ | | | | Υ | | | |
| ECG's ³ | | | | | | | | | | | |
| ECG Findings | Υ | | | Υ | | | | | | | |
| ECG Values | Υ | | | Υ | Υ | | | | | | |
| Vital Signs ³ | | | | | | | | | | | |
| Vitals Values | Υ | | | Υ | Υ | | | | | | |
| Spirometry | | | | | | | | | | | |
| Spiromtery | Υ | | | Υ | | | | | | | |
| Telemetry | | | | | | | | | | | |
| Telemetry Findings | Υ | | - | Υ | | | | | | | |

NOTES:

- T = Table, F = Figures, L = Listings, Y = Yes display generated.
- Summary = Represents TFL related to any summaries (i.e. descriptive statistics) of the observed raw data.
- Individual = Represents FL related to any displays of individual participant observed raw data.
- 1. Listings will include participant's numbers for individual AE's & AE system organ classes, preferred terms and verbatim text.
- 2. Chemistry summaries will include both changes from baseline & emergent results by PCI criteria.
- 3. Listings and summaries for ECGs and vital signs include treatment emergent PCI results

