5.2. Baseline Definitions

5.2.1. Baseline Definitions

For all endpoints (except as noted in baseline definitions) the baseline value will be the latest pre-dose assessment.

For tabulated safety summaries, only the scheduled assessments will be included in the summary tables.

| Parameter | Study Assessn | Study Assessments Considered as Baseline | | | | | | | | | |
|----------------------------------|---------------|--|----------------------|------------------|--|--|--|--|--|--|--|
| | Screening | Day -1 | Day 1 (Pre- Dose) | in Data Display | | | | | | | |
| Safety | | | | | | | | | | | |
| 12 Lead ECG & Vital Signs | Х | - | Х | Day 1 (Pre-Dose) | | | | | | | |
| Spirometry | Х | - | X | Day 1 (Pre-Dose) | | | | | | | |
| Haematology/Chemistry/Urinalysis | Х | X | - | Day - 1 | | | | | | | |
| Telemetry | - | - | X | Day 1 (Pre-Dose) | | | | | | | |

NOTES:

 Unless otherwise stated, the mean of replicate assessments at any given time point will be used as the value for that time point.

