| 3.42. | Bystander Safety (Part 1, Cohort C) | EG2 | Summary of Change from Baseline in ECG Values by Visit – Bystander | Only for Cohort C, Part 1. | SAC |
| 3.43. | Safety | Non-standard SAFE_T7 | Frequency of Maximum ECG Values by PCI Category – Part 1 | Compute and display Maximum by day. | SAC |
| 3.44. | Safety | Non-standard SAFE_T7 | Frequency of Maximum ECG Values by PCI Category – Part 2 | | SAC |
| 3.45. | Bystander Safety (Part 1, Cohort C) | Non-standard SAFE_T7 | Frequency of Maximum ECG Values by PCI Category – Bystander | Compute and display Maximum by day. Only for Cohort C, Part 1. | SAC |
| 3.46. | Safety | Non-standard SAFE_T8 | Frequency of Worst Change from Baseline Values of QTcB and QTcF by PCI Category – Part 1 | Compute and display Maximum by day. | SAC |
| 3.47. | Safety | Non-standard SAFE_T8 | Frequency of Worst Change from Baseline Values of QTcB and QTcF by PCI Category – Part 2 | | SAC |
| 3.48. | Bystander Safety (Part 1, Cohort C) | Non-standard SAFE_T8 | Frequency of Worst Change from Baseline Values of QTcB and QTcF by PCI Category – Bystander | Compute and display Maximum by day. Only for Cohort C, Part 1. | SAC |
| Vital Si | gns | | | | |
| 3.49. | Safety | VS1 | Summary of Vital Signs by Visit – Part 1 | This will not include Cohort C, Part 1. | SAC |
| 3.50. | Safety | VS1 | Summary of Vital Signs by Visit – Part 2 | | SAC |
| 3.51. | Bystander Safety (Part 1, Cohort C) | VS1 | Summary of Vital Signs by Visit – Bystander | Only for Cohort C, Part 1. | SAC |

| Safety: | Safety: Tables | | | | | | | |
|---------|---|-------------------------|---|---|---------------------------|--|--|--|
| No. | Population | IDSL / Example Shell | Title | Programming Notes | Deliverable [Priority] | | | |
| 3.52. | Safety | VS1 | Summary of Change from Baseline in Vital Signs by Visit – Part 1 | This will not include Cohort C, Part 1. | SAC | | | |
| 3.53. | Safety | VS1 | Summary of Change from Baseline in Vital Signs by Visit – Part 2 | | SAC | | | |
| 3.54. | Bystander Safety (Part 1, Cohort C) | VS1 | Summary of Change from Baseline in Vital Signs by Visit – Bystander | Only for Cohort C, Part 1. | SAC | | | |
| 3.55. | Safety | VS2 | Summary of Vital Signs by PCI – Part 1 | This will not include Cohort C, Part 1. | SAC | | | |
| 3.56. | Safety | VS2 | Summary of Vital Signs by PCI – Part 2 | | SAC | | | |

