| | Worst Post Baseline | n Increase<=30 30 <increase<=60 increase="">60</increase<=60> | 12 12(100%) 0 | 6 6(100%) 0 | 6 6(100%) 0 |

Example SAFE_T7
Protocol: 205822
Population: Safety

rotocol: 205822 Page 1 of 1

Table X
Frequency of Maximum ECG Values by PCI Category

| ECG Test | Visit | Category | Placebo (N=12) | 1 capsule - Single Dose | Single Dose |
|------------------------------------|------------------------|--|-------------------------------|----------------------------|------------------------|
| PR Interval, Aggregate (msec) | BASELINE | n | 12 | 6 | 6 |
| nggregate (mete) | | Value<110 110<=Value<=220 Value>220 | | 0 6(100%) 0 | 0 6(100%) 0 |
| | WORST POST BASELINE | n Value<110 110<=Value<=220 Value>220 | - | 6 0 6(100%) 0 | 6 0 6(100%) 0 |
| QRS Duration, Aggregate (msec) | SCREENING | n | 12 | 6 | 6 |
| 1199209000 (111000) | | Value<75 75<=Value<=110 Value>110 | , , | 0 6 (100%) 0 | 0 6(100%) 0 |
| | WORST POST BASELINE | n Value<75 75<=Value<=110 Value>110 | 12 0 11 (92%) 1 (8%) | 6 0 6(100%) 0 | 6 0 6(100%) 0 |
| QTcB Interval, Aggregate (msec) | SCREENING | n | 12 | 6 | 6 |

205822

| | Value<=450 | 11 (92%) | 6 (100%) | 6 (100%) |
|------------|--|----------|----------|----------|
| | 450 <value<480< td="">1 (8%)	0	0	</value<480<> | 1 (8%) | 0 | 0 |
| | 480<=Value<500 | 0 | 0 | 0 |
| | Value>=500 | 0 | 0 | 0 |
| WORST POST | n | 12 | 6 | 6 |
| BASELINE | Value<=450 | 11 (92%) | 5 (83%) | 6 (100%) |
| | 450 <value<480< td="">1 (8%)	1 (17%)	0	</value<480<> | 1 (8%) | 1 (17%) | 0 |
| | 480<=Value<500 | 0 | 0 | 0 |
| | Value>=500 | 0 | 0 | 0 |

Repeat for QTcF

Note: Percentages may not add up to 100 for QRS Duration and PR Interval as there is a possibility of a patient being counted under both low and high categories.

205822

Example : PK_T1 Page 1 of n : 205822

Population : Systemic PK

Table 3.1.13
Summary of Assessment of Dose Proportionality (Part 1 and Part 2)

| | | | Slope | | | _ | | | |
|-----------|-------|---|----------|----|--------|----------|----|--------|----------------|
| Parameter | Study | n | Estimate | SE | 90% CI | Estimate | SE | 90% CI | Coefficient of |
| | Day | | | | | | | | Determination |

Note(s): CI = confidence interval; SE = standard error.

Source: SAS Output XX

205822

Example : PK_T2 Page 1 of n

Protocol : 205822 Population : Systemic PK

Table 3.1.16 Summary of Assessment of Steady State (Part 1 and Part 2)

| | | | Slope | Slope | | | | |

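### Shell SAFE_T7 sets QRS and QTc against Screening, not the plan's pre-dose baseline, so an ECG value that crosses a PCI limit between screening and first dose is shown against the wrong reference

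*SAP*

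**What the plan says.** - **Promise.** Note 3 to Table 3 (SAP Section 7): "Listings and summaries for ECGs and vital signs include treatment emergent PCI results".
- **Baseline rule.** SAP Section 5.2.1: "For all endpoints (except as noted in baseline definitions) the baseline value will be the latest pre-dose assessment". In the table below that rule, the line for "12 Lead ECG & Vital Signs" marks Screening and Day 1 pre-dose as eligible, puts a dash under Day -1, and names Day 1 (Pre-Dose) as the baseline used in displays. Section 5.2.2 applies these definitions unless something else is specified.
- **Display.** SAP Section 11.10.5 assigns Tables 3.43 to 3.45 to shell SAFE_T7; the first is titled "Frequency of Maximum ECG Values by PCI Category – Part 1".
- **Shell.** In SAP Section 11.11, SAFE_T7 opens its blocks with "PR Interval, Aggregate (msec) | BASELINE", "QRS Duration, Aggregate (msec) | SCREENING" and "QTcB Interval, Aggregate (msec) | SCREENING". Each is followed by a worst-post-baseline block. A closing instruction repeats the QTcB layout for QTcF.
- **Sibling shell.** The shell for worst change in QTcB and QTcF uses Baseline for both. It is printed as SAFE_T6, although the display list calls it SAFE_T8.

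**The concern.** A reader of a PCI table compares the row before treatment with the row after it. If the first row is not the plan's baseline, that comparison does not answer the question that note 3 raises, namely what emerged on treatment. Within SAFE_T7 the reference differs by parameter, and no reason is given. QTc, usually the ECG measure of most interest, gets the older reference.

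ECG is among the primary safety endpoints (Section 2.2), and the groups are small. The dummy shells in Section 11.11 show columns of 4, 6 and 12 participants, so one participant placed against the wrong reference is 25%, 17% or 8% of a column.

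**Working it through.** The plan gives no figure for this point, so the check sets the texts side by side and then follows what the Screening row does.

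**1. Reference row by source**

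| Source | PR | QRS | QTcB | QTcF |
|---|---|---|---|---|
| Section 5.2.1 | Day 1 pre-dose | Day 1 pre-dose | Day 1 pre-dose | Day 1 pre-dose |
| SAFE_T7 | Baseline | Screening | Screening | Screening (repeat of QTcB) |
| QTc-change shell | not shown | not shown | Baseline | Baseline |

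SAFE_T7 disagrees with Section 5.2.1, with its sibling and with its own PR block. The programming notes for Tables 3.43 to 3.45 do not correct the row.

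**2. What the Screening row does.** Let N be normal and A be beyond a PCI limit, in the order screening / last pre-dose / worst post-dose.

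| Pattern | Seen with a Screening row | Seen with the 5.2.1 baseline row |
|---|---|---|
| N/N/A | new | new |
| A/A/A | already present | already present |
| N/A/A | looks new | already present |
| A/N/A | looks already present | new |

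Only the last two patterns are misread, and they err in opposite directions. The post-dose count is the same in both columns.

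**3. Does relabelling alone deliver note 3?** No. SAFE_T7 gives two separate frequency blocks and does not link participants between them. In its dummy placebo column, 1 of 12 (8%) has QTcB above 450 and below 480 msec at screening and 1 of 12 (8%) after baseline; nothing shows whether this is the same person. Appendix 3 (Section 11.3.2) defines treatment states by onset for adverse events only. No rule says when a PCI value is treatment emergent, and this affects PR as well.

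**4. Does the Section 5.2.1 baseline exist in every cohort?** As printed in Section 11.2.1:

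| Schedule | Day -1 ECG | First Day 1 ECG |
|---|---|---|
| Single dose | none | pre-dose, triplicate |
| Repeat dose (other than Cohort A Part 1) | triplicate | 2 h after the morning dose |
| Bystanders (Cohort C) | triplicate | 2 h after exposure |

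For the last two rows, the general rule (latest pre-dose assessment) points to Day -1. The ECG line of 5.2.1 excludes Day -1 and names a Day 1 pre-dose ECG that is not scheduled. Of the assessments that line allows, only Screening is then left.

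**5. Illustration of size.** The SAP gives no QTc variance, so every input here is an assumption: between-participant SD 15 msec, between-day SD d of 6 or 10, single-reading SD 6, a single screening reading S, and a pre-dose value D that is the mean of three.

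Var(S) = 15² + d² + 6² = 297 (d = 6) or 361 (d = 10). Var(D) = 15² + d² + 6²/3 = 273 or 337. Cov(S, D) = 15² = 225. Bivariate normal probabilities for the 450 msec limit are:

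| Mean QTc | S ≤ 450 and D > 450 | S > 450 and D ≤ 450 |
|---|---|---|
| 410 | 0.46–1.06% | 0.70–1.36% |
| 420 | 1.7–3.2% | 2.4–3.8% |
| 430 | 4.6–7.1% | 5.6–7.9% |

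Among participants at or below 450 at screening, the chance p of being above 450 pre-dose is 0.5–1.1%, 1.8–3.4% and 5.2–8.3% for the three means. The chance of at least one among 12 is 1 − (1 − p)^12; for p = 1.82% this is 1 − 0.9818^12 = 20%. Over all scenarios it runs from 5% to 65%; for 6 participants, from 3% to 41%. These figures cover the pre-dose crossing only. The value must also be abnormal post-dose to be misread in the table.

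**The case against.** **Status of the shell.** SAFE_T7 is headed as an example, holds dummy data and, like its neighbour, appears to be carried over from elsewhere: the QTc-change shell has a column for a product label not listed in Section 5.1. Section 5.2.2 makes the 5.2.1 baselines the default, and no hypothesis is tested. This limits the weight of the point. It does not remove it, because the display list sends the tables to this shell and a programmer following it would build the Screening rows.

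**Other displays.** Tables 3.40 to 3.42 give change from baseline, Tables 3.46 to 3.48 give worst QTc change by category, and Listings 55 to 57 print all ECG values for anyone with a PCI value. A careful reader could find a pre-dose abnormality there. This stands as partial protection.

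**The stronger readings.** A reader might infer that every abnormality present before dosing will appear as emerging on drug. That is not so: one present at screening is visible in the Screening row. A reader might also infer that emergent counts by dose are inflated. SAFE_T7 contains no emergent count, and its post-baseline counts do not depend on the reference row. Inflation would be the expected direction only if entry required a normal screening ECG. Such a limit would sit in the protocol, which is not at hand. Without one, the illustration makes the masking pattern slightly more frequent in every scenario.

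**Conclusion.** The inconsistency is plain in the text: for QRS, QTcB and QTcF, SAFE_T7 uses a reference that Section 5.2.1 does not allow where a later pre-dose ECG exists. The consequence is confined to participants who cross a PCI limit, in either direction, between screening (up to 30 or 45 days before Day 1) and first dose. For them the table can present a pre-drug abnormality as new, or a new one as old.

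The document does not support a net direction or a size. The assumed-variance range of 5% to 65% for at least one upward crossing among 12 shows how far the answer depends on inputs the plan does not give. No inferential result changes.

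Two linked gaps rest on the text alone: the baseline does not resolve for the repeat-dose and bystander schedules, and a treatment-emergent PCI value is promised but not defined. The point is a modest one that should be settled before the tables are programmed.

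**What to change.** 1. In SAFE_T7, use the Section 5.2.1 baseline (latest pre-dose assessment) as the reference row for PR, QRS, QTcB and QTcF. Keep Screening at most as an extra row.
2. Reconcile the ECG line of Section 5.2.1 with the repeat-dose and bystander schedules in Section 11.2.1, so that baseline resolves to the latest pre-dose ECG actually taken in every cohort. Adjust the display label to match.
3. Define a treatment-emergent PCI value: in the category post-dose and not in it at baseline. Report it in Tables 3.43 to 3.45 as a count or a shift from baseline, so that note 3 to Table 3 is met.
4. In the same edit, align the number of the QTc-change shell (SAFE_T6 in Section 11.11, SAFE_T8 in Section 11.10.5).

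The cost is minor shell and programming work. The ECGs are already scheduled, so no new data are needed.

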7.1. Study Medication Exposure

Exposure to study medication as the number of doses administered will be presented for each treatment for each Part.

7.2. Adverse Events Analyses

Adverse Events will be coded using Medical Dictionary for Regulatory Activities (MedDRA) central coding dictionary, Version 21.0.

See Appendix 3: Study Phases and Treatment Emergent Adverse Events to determine treatment states for AE data. Handling of partial dates for AEs is outlined in Appendix 6: Reporting Standards for Missing Data. In the rare case when it is not possible to assess treatment emergence, the AE will be classified as treatment emergent (i.e. the worst case).

AE Severity is classified as mild (grade = 1), moderate (grade = 2), or severe (grade = 3). AEs with a missing severity will be classified as severe. If a participant reports an AE more than once within that SOC (System Organ Class)/ PT (Preferred Term), the AE with the worst case severity will be used in the corresponding severity summaries.

Relationship to study treatment, as indicated by the Investigator, is classified as "not related" or "related". AEs with a missing relationship to study medication will be regarded as "related" to study medication.

All AE tabulations will be performed separately for Part 1 and Part 2, by dose, and will include the number and percentage of participants. For each study part and cohort, incidence of AEs will be tabulated by the following:

- All AEs by SOC and PT
- All related AEs by SOC and PT
- All AEs by SOC, PT and Severity
- All related AEs by SOC, PT and Severity

All AEs leading to permanent discontinuation of study treatment will be identified by using the variable pertaining to outcome on the Adverse Events page of the CRF, and listed separately for each study part and cohort.

Serious adverse events (SAEs) are those events recorded as "Serious" on the Adverse Events page of the CRF, and will be listed separately for each study part.

The details of the planned displays are provided in Appendix 11: List of Data Displays.

